### 3.0 SCHEMA

- 3.1** Patients who meet the enrollment criteria will be enrolled following the decision to proceed with RT for pathologically proven prostate adenocarcinoma. N=10 patients will be enrolled in the study.
- 3.2** Baseline urinary symptoms, rectal symptoms, sexual function, and global quality of life will be assessed using validated patient-reported questionnaires.
- 3.3** A 3-Tesla pelvic MRI containing an axial T2 sequence will be performed without a rectal coil. The use of IV contrast is at the discretion of the treating physician. If an MRI obtained within 3 months prior to enrollment

is deemed clinically acceptable for treatment purposes by the treating physician then reacquisition is not necessary.

- 3.4** CT simulation will be performed with a Foley catheter in place. Radiopaque dummy seeds will be used to mark the anticipated location of the radiotransponder beacons within the catheter.
- 3.5** Utilizing available clinical data (biopsy, physical exam, MRI/MRS, and CT-simulation) physicians, medical dosimetrists, and physicists will create and approve a treatment plan if all dosimetric and quality assurance measurements are met (see sections 6.3 – 6.5). Prescribed dose will be 8.0 Gy per fraction for a total of 5 fractions.
- 3.6** SBRT will be delivered in 9 to 17 calendar days, with every other day fashion in an outpatient clinic setting with an every-other day fashion treatment schedule (see section 6.8). Intraurethral radiotransponder guidance will be performed for all treatments (see section 6.6.4).
- 3.7** Following completion of treatment, patients will be evaluated with clinical exams, laboratory PSA testing, and quality-of-life questionnaires at regular intervals (1, 3, 6, 9, 12, 18, and 24 months post-radiation)
- 3.8** Post-treatment multiparametric MRI and biopsy 1 year from completion of SBRT.

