### 6.3 SBRT dose specifications

- 6.3.1 The prescribed dose will be 40 Gy to the PTV, delivered at 8.0 Gy per fraction for a total of 5 fractions.
- 6.3.2 At least 95% of the PTV should receive 100% of the prescribed dose.
  - 6.3.2.1 Coverage of 90-95% of the PTV by 100% of the prescribed dose will be considered a minor but acceptable deviation whereas coverage of <90% by 100% of the prescription dose will be considered a major unacceptable deviation.
- 6.3.3 Rapid dose falloff outside the PTV is to be prioritized over PTV dose uniformity and may result in considerable dose heterogeneity within the PTV, but the maximum dose within the PTV should be limited to 130% of the prescription.

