### **9.2 Technical feasibility**

For the purposes of this study, technical feasibility encompasses two major components: implementation of the intraurethral radiotransponder motion management technique and treatment planning and treatment delivery of single fraction focal SBRT. Treatment planning includes integration of clinical data (exam, biopsy, and medical imaging) to create targets for radiotherapy treatment. Treatment delivery includes the ability to administer planned radiotherapy dose accurately, including pre-treatment physics quality assurance and accurate patient positioning and image guidance.

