### **9.2.2 Treatment planning feasibility**

The treatment planning feasibility will be determined by the ability of the treating physician and involved dosimetrists and physicists to produce a radiotherapy treatment plan that meets the specifications in section 6.3 and 6.4.

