## **9.3 Treatment delivery**

9.3.1 All treatment plan dose distributions will be verified by UAB staff physicists and must meet the quality assurance standards set forth by the Department of Radiation Oncology prior to patient SBRT administration. Pre-treatment tissue phantom quality assurance checks will be completed. The phantom will be irradiated with the same plan as the patient including all couch angles and beam projections. A dose plane will be calculated and exported from the treatment planning system and will be compared with the measured dose plane from the one of the above techniques. Dose comparisons will be analyzed using the gamma criteria of 3%/3mm and will be considered valid if 95% of points have gamma values of less than 1.

Once plans have met physics quality assurance parameters, treatment delivery will commence. Clinical treatment delivery feasibility will be determined by the ability of the patient to be set up accurately with confirmation of appropriate geometry on kilovoltage imaging.

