## **11.0 STATISTICAL CONSIDERATIONS**

### **11.1 Endpoints and measure of success**

- 11.1.1 The primary endpoint of the pilot portion of this study is feasibility of focal treatment using the intra-urethral radiotransponder beacon technique as defined in section 9.2.
- 11.1.2 This pilot study will be considered successful if at least 9 of 10 patients who begin treatment are able to complete treatment using the described technique.

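### The primary endpoint covers simulation and planning, but the 9-of-10 success rule scores only patients who begin treatment, so a failure before the first fraction is not counted as one

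*Combined protocol and SAP*

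**What the plan says.** **Endpoint.** Section 11.1.1 sets the primary endpoint as "feasibility of focal treatment using the intra-urethral radiotransponder beacon technique as defined in section 9.2". Section 9.2 has two components: the intra-urethral transponder technique, and "treatment planning and treatment delivery of single fraction focal SBRT". (The single-fraction wording does not match the five fractions of 6.3.1; nothing here turns on that.) Section 9.2.2 judges planning by whether the team can "produce a radiotherapy treatment plan that meets the specifications in section 6.3 and 6.4". The first criterion in 9.2.1 is whether beacon positions can be predicted from the simulation CT, which under 6.2.1 is done with a Foley catheter and dummy seeds in place.

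**Success rule.** Section 11.1.2 calls the study successful if "at least 9 of 10 patients who begin treatment are able to complete treatment using the described technique". Section 11.6.1 repeats this and computes its intervals on 10 patients.

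**Order of events.** Section 3.1 states "N=10 patients will be enrolled in the study" and places enrolment after the decision to give radiotherapy. Simulation (3.4) and planning (3.5) follow. Under 3.5 the team will "create and approve a treatment plan if all dosimetric and quality assurance measurements are met". PTV coverage below 90% "will be considered a major unacceptable deviation" (6.3.2.1). Section 9.3.1 adds: "Once plans have met physics quality assurance parameters, treatment delivery will commence".

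**The concern.** The endpoint and its rule cover different stretches of the patient's course. Simulation and planning belong to the endpoint, but they are over before anyone can begin treatment. A patient lost at either step has failed a named component of feasibility, yet the rule does not score him, and planning has no threshold of its own elsewhere in Section 11.

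Sections 3.1 and 11.6.1 enrol 10, and the rule then speaks of 10 who begin treatment. The two tens agree only if every enrolled patient starts. Once one does not, the plan does not say whether 9 remains a fixed count, becomes 90% of those who started, or applies after replacement. This is the study's only success criterion for its primary objective, so the same data could be reported as success or failure depending on a reading chosen afterwards.

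**Working it through.** **Inputs.** 10 enrolled (3.1, 11.6.1); at least 9 of 10 starters completing (11.1.2); exact 95% intervals for proportions (11.5.1). No failure rate is assumed: the cases below are illustrations.

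**Formula.** Clopper-Pearson, x successes in n: lower = Beta quantile at 0.025 with parameters (x, n−x+1); upper = Beta quantile at 0.975 with parameters (x+1, n−x). When x = n, the lower limit is 0.025^(1/n) and the upper limit is 1.

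**The plan's own figures (11.6.1).**
- 9/10: 0.5550 to 0.9975, width 0.9975 − 0.5550 = 0.4425. Matches.
- 10/10: lower limit 0.025^(1/10) = 0.6915. Matches.

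The stated arithmetic is right. The question is what the 10 refers to.

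**Where a failure is scored.**

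| Step | Part of the endpoint? | Scored by 11.1.2? |
|---|---|---|
| Simulation with catheter and dummy seeds (6.2.1, 9.2.1) | Yes | No: before treatment |
| Plan meeting 6.3 and 6.4 (9.2.2) | Yes | No: before treatment |
| Completing delivery with the technique | Yes | Yes |

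**Case A: two pre-treatment failures; everyone who starts completes.**
- Fixed count, no replacement: 10 − 2 = 8 completers, fewer than 9. Not met.
- Percentage of starters: 8/8 = 100%, lower limit 0.025^(1/8) = 0.6306. Met.
- Both replaced: 10/10, lower limit 0.6915. Met.
- All enrolled: 8/10 = 80% (0.4439 to 0.9748), or with replacement 10/12 = 83.3% (0.5159 to 0.9791). Below 90% either way.

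**Case B: one pre-treatment failure and one treated patient who does not complete.**
- No replacement: 8 completers among 9 starters. The fixed count is missed, and 8/9 = 88.9% is also below 90%; 8/10 of those enrolled is below it too. All readings agree.
- Replaced: 9/10 starters (0.5550 to 0.9975), met; but 9/11 = 81.8% of those enrolled (0.4822 to 0.9772), below 90%.

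**Case C: one pre-treatment failure; everyone who starts completes.**
- No replacement: 9 completers, 9/9 starters (lower limit 0.6637), 9/10 enrolled (0.5550 to 0.9975). Met on every reading.
- Replaced: 10/10 starters (lower limit 0.6915), 10/11 = 90.9% enrolled (0.5872 to 0.9977). Met on both.
- Only the reported estimate changes.

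The conclusion therefore differs between readings in Case A, and in Case B only if the lost patient is replaced.

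**The case against.** The strongest reply is that the rule is a count. Enrolment is fixed at 10 and 11.6.1 works on n = 10, so nine completers are needed and two planning failures already sink the study, which is the verdict that 8/10 gives. This limits the point. A reader might infer that the rule as written would declare success at 8/8. The documents do not support that: it needs the count to be recast as a percentage. They do not state the fixed-count reading either, so what stands is ambiguity, plus the fact that no reading scores the pre-treatment failure itself.

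Second, 10/10 against 10/12, and 9/10 against 9/11, need replacement, and the available text provides for none. Section 10.0 (Patient Registration) was not available to this review and may address it. This stands, and nobody should infer that replacement is planned. Replacement would settle the number of starters, but the replaced failure would still be uncounted unless the rule said otherwise.

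Third, planning failure may be rare. Coverage of 90–95% is acceptable (6.3.2.1), and the 6.4 limits are guidelines carried over from the institution's earlier protocol with a 40 Gy focal boost. On the other side, the 3 mm PTV margin (6.2.5) can reach the urethra, where the maximum is 38.78 Gy against a 40 Gy prescription. Failure is conceivable, but the documents do not show how often, and it should not be inferred that it is likely.

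Fourth, beacon guidance is exercised only in treated patients, and the analysis is descriptive, so no error rate is affected. Both are true. They would justify a rule about delivery alone, but 11.1.1 adopts all of 9.2, and 9.2.2 is given a criterion without a threshold.

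**Conclusion.** The concern holds as a mismatch between endpoint and rule. The endpoint includes simulation-based beacon localisation and planning; the rule counts only patients who begin treatment; a failure between enrolment and the first fraction is not scored as one. With fewer than 10 starters the rule has no single meaning, and two such failures, with all others completing, are enough for the readings to disagree: impossible to meet, 8/8, or 10/10, against 80% or 83.3% of enrolled patients. A single failure with all others completing alters the estimate but not the conclusion.

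This rests on the order of steps in 3.1 to 3.5 and on the absence of a replacement rule from the available text. It does not show that the study would be wrongly declared successful, or that planning failures are to be expected. It is worth correcting because it bears on the only success criterion; it is not a safety matter.

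**What to change.** In 11.1.2 and 11.6.1:

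- **Denominator:** all enrolled patients, excluding only those who withdraw or prove ineligible before CT simulation for reasons unrelated to the technique. Restricting it to patients who reach planning would still omit a man who cannot complete simulation with the catheter.
- **Threshold:** 90% or more, that is, at least 9 of 10. If replacement takes enrolment past 10, this means 10 of 11 (90.9%) or 11 of 12 (91.7%).
- **Per-patient success:** simulation completed with the catheter, a plan approved under 3.5 with no major deviation under 6.3.2.1, and all 5 fractions completed with the beacon technique.
- **Pre-treatment failures:** a simulation or planning failure counts as a failure even if the patient is replaced. State whether replacement is allowed.
- **Reporting:** list simulation, planning and delivery failures separately, and report attainment of each 6.4 limit descriptively. Say explicitly that a missed 6.4 limit alone is not a failure: 6.4 calls its limits guidelines, whereas 3.5 and 9.2.2 read literally would require every one to be met.

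The cost is a few sentences and no new data, since dose-volume results exist from planning. The success count may be less favourable, and a planning failure unrelated to the beacons would count against the combined result. The separate listing lets readers see when that has happened.

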### **11.2 Secondary endpoints include clinical toxicity and efficacy assessments.**

- 11.2.1 Clinically assess early toxicity, early efficacy, late toxicity, and quality of life for patients receiving focal prostate SBRT.

### **11.3 Toxicity evaluation**

- 11.3.1 Acute and late toxicity will be graded per the Common Terminology Criteria for Adverse Events version 4.0 (CTCAE v4.0,

[http://evs.nci.nih.gov/ftp1/CTCAE/CTCAE\\_4.03\\_2010-06-14\\_QuickReference\\_5x7.pdf](http://evs.nci.nih.gov/ftp1/CTCAE/CTCAE_4.03_2010-06-14_QuickReference_5x7.pdf).

- 11.3.2 Definition of acute toxicity: any possible, probable, or definite treatment-related AE or SAE occurring within three months of the completion of radiotherapy.
- 11.3.3 Definition of late toxicity: any possible, probable, or definite treatment-related AE or SAE occurring after three months of the completion of radiotherapy.

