#### **7.4 Guidelines for adverse event recording**

**7.4.1** The Common Terminology Criteria for Adverse Events version 4.0 (CTCAE v4.0, [http://evs.nci.nih.gov/ftp1/CTCAE/CTCAE\\_4.03\\_2010-06-14\\_QuickReference\\_5x7.pdf](http://evs.nci.nih.gov/ftp1/CTCAE/CTCAE_4.03_2010-06-14_QuickReference_5x7.pdf)) will be used for grading adverse events

**7.4.2** The investigator must assess the relationship of any AE or SAE to the use of study treatment using the following guidelines outlined in the table below:

Table 7.5.3 ATTRIBUTION OF ADVERSE EVENTS		
Code	Descriptor	Definition
5	Definite	The adverse event is clearly related to the investigational treatment
4	Probable	The adverse event is likely related to the investigational treatment
3	Possible	The adverse event may be related to the investigational treatment

2	Unlikely	The adverse event is doubtfully related to the investigational treatment
1	Unrelated	The adverse event clearly not related to the investigational treatment

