## 8.0 STUDY PARAMETERS

- 8.1** For the purposes of this study, acute toxicity will be defined as event(s) that occur within 90 days of the completion of radiotherapy. Acute toxicity will be determined by both intra-treatment examinations and by scheduled follow-up evaluations after the treatment has completed. Late toxicity will be defined as any toxicity occurring > 90 days after the completion of treatment.
- 8.2** Baseline evaluations of enrolled patients must occur within six weeks of study enrollment
- 8.3** "Day 1" will be defined as the date of the first radiotherapy treatment. "Day 42/Week 5/Month 1" will represent the one month follow-up visit after the completion of the last radiotherapy treatment. Day 1 and Day 43/Week 5/Month 1 evaluations may be done within +/- 7 days of the specified day.
- 8.4** "Month 1, 3, 6, 9, 12, 18, and 24" will be defined as the respective follow up visits after the completion of radiotherapy. Month 3-24 evaluations may be done within +/- 30 days of the specified day.

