**Table 8.1 Required evaluations and therapies**

	Baseline	Week 1-2	Week 5/Mo 1	Mo 3, 6, 9, 12, 18, 24
PSA	x+		x	x
H and P**	x^		x^	x^
Karnofsky PS	x		x	x
Platelet count or CBC	x			
Quality of Life Indices/Questionnaires*/**	x	x#, ^	x	x
CTCAE v4.0 Toxicity Grading	x	x	x	x
SBRT		xxxxx		
Prostate Biopsy	x			Month 12

\* AUA Symptom Score, SHIM, and EPIC questionnaire - Appendix

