## **9.4 Treatment phase**

- 9.4.1 The patient will be evaluated at least once by the treating physician during the time that he is undergoing radiotherapy treatment.
- 9.4.2 On the final day of treatment the patient will complete an AUA symptom score, SHIM, and EPIC questionnaires and the treating physician will give toxicity grades for any toxicity present at the time.

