## **9.5 Follow-up**

- 9.5.1 As outlined in section 8.0, follow-up examinations will occur at regularly scheduled intervals, occurring every three months for one year and then every six months at the year one to two interval in order to appropriately monitor acute and late toxicity, quality of life, and PSA response.
- 9.5.2 For each follow up visit, the treating physician will complete an updated medical history and perform a physical examination, evaluate KPS, and grade any toxicity noted. Symptom score surveys and questionnaires will be completed by the patient and PSA lab draws will be performed. Some of these study procedures may be conducted remotely, if necessary.

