#### **11.5 Statistical Analyses**

- 11.5.1 All statistical analyses will be descriptive. No formal statistical comparisons are planned. Descriptive statistics will be calculated at baseline and at various follow-up time points as indicated in Table 8.1 (“Required evaluations and therapies”). These include means, standard deviations, medians, and ranges for continuous variables and frequencies and percentages for categorical variables. In addition, 95% confidence intervals will be calculated for means and exact binomial 95% confidence intervals will be calculated for proportions (such as toxicity rates).
- 11.5.2 Continuous variables include PSA measurements and the composite scores from all three quality of life questionnaires, i.e. the composite AUA Symptom Score, the composite SHIM score, and the composite EPIC score. Categorical variables include toxicity results and biopsy results.
- 11.5.3 Statistical analyses will be performed using SAS, version 9.4 or later (SAS Institute, Inc.; Cary, NC).

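### Section 11.3 defines toxicity by attribution, with no rule for worsening from the baseline CTCAE grade, and read with 7.3.1 it leaves out typical grade 1–2 urinary and GI events

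*Combined protocol and SAP*

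**What the plan says.** **Definitions.** Section 11.3.2 defines acute toxicity as "any possible, probable, or definite treatment-related AE or SAE occurring within three months of the completion of radiotherapy", and 11.3.3 defines late toxicity as "any possible, probable, or definite treatment-related AE or SAE occurring after three months of the completion of radiotherapy". Section 8.1 gives a different rule: "acute toxicity will be defined as event(s) that occur within 90 days of the completion of radiotherapy". Its late definition covers any toxicity after 90 days. Neither part of 8.1 mentions attribution.

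**Attribution.** Section 7.4.2 states that "The investigator must assess the relationship of any AE or SAE to the use of study treatment", on a five-level scale. Codes 3 to 5 (possible, probable, definite) pass the 11.3 filter. Codes 1 and 2 (unrelated, unlikely) do not.

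**Grading.** Table 8.1 marks the row "CTCAE v4.0 Toxicity Grading" at baseline, during weeks 1–2, at month 1 and at every later visit. On the last treatment day "the treating physician will give toxicity grades for any toxicity present at the time" (9.4.2). At follow-up the same physician is to "evaluate KPS, and grade any toxicity noted" (9.5.2). Neither instruction refers back to baseline.

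**Analysis.** Section 11.5.1 says "Descriptive statistics will be calculated at baseline and at various follow-up time points as indicated in Table 8.1", and 11.5.2 lists toxicity among the categorical variables.

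**AE and SAE.** Section 7.3.1 includes new illness and worsening of existing conditions among AEs. It then takes typical radiotherapy symptoms out of the AE definition, naming urinary and GI toxicity of grade 3 or lower, while requiring that they be documented. Section 7.3.2 makes any urinary or GI toxicity of grade 3 or higher an SAE.

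**The concern.** Toxicity is a stated secondary endpoint, and lower toxicity is the main argument for focal treatment (2.2, 2.5). A single-arm study has no control group to show how often urinary, bowel or sexual symptoms would arise anyway, so each man's own baseline is the natural reference. Symptoms at entry are to be expected: only AUA scores of 18 or more are excluded (4.2.4), continued alpha-blocker use is allowed (7.2.4), and section 4 sets no entry limit on sexual function. The baseline grade is collected, yet the endpoint rests on a causal judgement instead.

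The second problem concerns which events reach that judgement. Section 11.3 counts only AEs and SAEs, and 7.3.1 removes typical urinary and GI toxicity from the AE category. Section 2.5 names grade 2 late effects as the common complications of whole-gland SBRT that a smaller irradiated volume may reduce. Under a literal reading, the events of most interest are not in the count.

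**Working it through.** **1. The plan's own figures.** Section 11.6 gives exact intervals for feasibility only; no toxicity figure is stated. The Clopper–Pearson 95% limits for x of n are: lower = Beta quantile at 0.025 with parameters (x, n−x+1); upper = Beta quantile at 0.975 with parameters (x+1, n−x). For 9/10 this gives (0.5550, 0.9975), width 0.4425. For 10/10 the lower limit is 0.025^(1/10) = 0.6915. All agree with 11.6.

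**2. What each section counts, read literally, for a typical urinary or GI symptom.**

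| Grade | AE under 7.3.1? | SAE under 7.3.2? | Counted by 11.3? | Counted by 8.1? |
|---|---|---|---|---|
| 1–2 | No | Only with death, inpatient stay or transfusion | No, unless an SAE | Yes |
| 3 | No | Yes | Yes, if possible or higher | Yes |
| 4 or more | Yes | Yes | Yes, if possible or higher | Yes |

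Two consequences follow.
- Section 7.4.2 requires attribution only for AEs and SAEs, so the grade 1–2 events may have no code to which the 11.3 filter could be applied.
- The note in 7.3.2 classes urinary retention needing a temporary catheter as grade 2. If it is regarded as a typical symptom, 11.3 omits it, although section 2.4 reports it as the primary safety endpoint of the institution's previous SBRT trial.

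**3. What the 11.5 tables can show.** Suppose 3 of 10 men have a given symptom at baseline and 3 of 10 have it at month 3 (counts chosen for illustration). The number newly affected lies between 0 (the same three men) and min(3, 10−3) = 3 (three different men). The two tables are identical in both cases. The within-patient result runs from 0/10 (95% CI 0 to 0.3085) to 3/10 (0.0667 to 0.6525).

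**4. Size of one reclassification.** With n=10 each man is 1/10 = 10 points:
- 0/10: 0 to 0.3085
- 1/10: 0.0025 to 0.4450
- 2/10: 0.0252 to 0.5561

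For scale, section 2.5 gives whole-gland grade 2 late rates of 5% to 15% across hematochezia, diarrhea, hematuria and stricture with retention. If those rates applied here (an assumption; focal treatment is expected to do better), 10 men would give 10 × 0.05 = 0.5 to 10 × 0.15 = 1.5 cases per term. One man gained or lost is about as large as the expected count.

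**The case against.** Several stronger readings are tempting, and the documents do not support them.

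- A reader might infer that the baseline grade is never used. Section 11.5 would tabulate it. What is missing is a rule comparing each man with his own baseline.
- A reader might infer that the treating physician decides causality. Section 7.4.2 names the investigator; the treating physician grades. They may be the same person, but the text does not say so.
- A reader might infer that an unchanged grade 2 urinary symptom would be counted as toxicity. The AE wording in 7.3.1 points to new onset or worsening, and typical symptoms of that grade are excluded in any case. An AUA score of up to 17 at entry shows that symptoms are possible, not that men enter at CTCAE grade 2.
- A reader might infer that new events are readily dismissed on attribution. The filter is inclusive: an event must be rated unlikely or unrelated to be dropped.

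Other defences carry weight. CTCAE grading is itself unblinded clinical judgement, so a comparison with baseline is not fully objective; it removes only the added causal step. AUA, SHIM and EPIC scores are collected at baseline and afterwards without attribution, and partly cover urinary, bowel and sexual change. The 7.3.1 exclusion may have been meant only to limit AE reporting, since the events are still documented. An unfiltered count over 24 months will pick up some unrelated illness. No test or success threshold depends on toxicity.

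These points limit the concern but do not remove it. Sections 8.1 and 11.3 still define one endpoint in two ways, no rule uses the baseline grade to define worsening, and 11.3 as written does not count typical grade 1–2 urinary and GI events.

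**Conclusion.** The point holds as a modest but worthwhile correction. The toxicity endpoint has two inconsistent definitions. The one in the statistical section ignores each man's baseline grade and, combined with 7.3.1, leaves out the lower-grade events that the rationale is about. The loss of grade 1–2 events depends on reading 7.3.1 and 11.3 literally; an analyst following 8.1 would count them.

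Each reclassified man moves a rate by 10 points. The documents give no basis for saying how many would be reclassified, or whether the net effect would raise or lower the reported rates. The consequence is confined to a descriptive secondary endpoint: the feasibility criterion of 9 of 10, its interval and N=10 are unaffected.

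**What to change.** 1. In 11.3 and 11.5, make the main summary the number of men whose worst grade for a CTCAE term exceeds their own baseline grade, whatever the attribution and whether or not the event is classed as an AE. Cover urinary, GI and sexual terms at minimum. Present it by grade with the exact 95% CI.
2. Report the acute (within 90 days) and late (after 90 days) periods separately, since a single worst grade would merge them. Allocate by date: the month 3 visit has a ±30-day window (8.4) and can fall on either side of day 90.
3. Show the attributed-only count (possible or higher) in an adjacent column.
4. Reconcile 7.3.1, 7.3.2, 8.1 and 11.3 so that one definition applies. Add CTCAE grading to the baseline list in 9.1, which omits it although Table 8.1 requires it.

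The cost is protocol wording and one extra table column; Table 8.1 already requires the grades. The unfiltered rate may be higher than the attributed one because it includes some unrelated events, and the adjacent column lets the reader see the difference.
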